Despite insufficient response after 3 to 6 months therapy, treat-to-target recommendations of EULAR were only applied in 50% of the German course and prognosis of early arthritis cohort (CAPEA).[14] In an analysis of a cohort from the “Kerndokumentation”, a national database of the German Collaborative Arthritis Centres, 45% of patients were not within DAS28 low disease activity range and therefore would have needed adaption of therapy according to current treatment guidelines. In contrast, rheumatologists’ global assessment of disease activity differed, 80% perceived their patients to be in the low disease activity range and, hence, as being adequately treated.[15]

These observations suggest that in a real-world setting, criteria other than calculated DAS28 remission or low disease activity alone may guide treatment decisions. Among such criteria, satisfaction with drug treatment is of particular interest. On the one hand, a patient who is content with his current therapy is less likely to be willing to change a therapy solely to achieve a better DAS28 score. On the other hand, patient preference and satisfaction of a therapy strongly affects adherence to a prescribed medication, ultimately affecting treatment outcome and efficacy. A factor known to impact on patient satisfaction with a prescribed treatment is the route of administration. Here, several studies point to a preference for oral therapies, also among second-line DMARDs.[16,17]

Recently, Tofacitinib, an orally applied DMARD of the new class called Janus-Kinase-Inhibitors (JAK-Inhibitors) has been brought into the market in the European Union. Tofacitinib is indicated in combination with methotrexate (MTX) for the treatment of moderate to severe active rheumatoid arthritis (RA) in adult patients who have responded inadequately to, or who are intolerant to one or more DMARD. Due to oral administration of Tofacitinib, the impact of patient’s satisfaction with drug treatment on therapy decisions by rheumatologists may be especially pronounced.

EULAR recommendations have now endorsed individual patient related factors such as patient preferences and comorbidities as an overarching principle in the management of RA.

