7.3. Variables

Variable	Role	Data source(s)	Operational definition
RA-treatment with Tofacitinib and/or other DMARDs - date of initiation	Exposure, Potential confounder, subgroup identifier	Case records and electronic Case Report Form (eCRF)	Details will be provided in Statistical Analysis Plan
RA treatment with Tofacitinib and/or other DMARDs – dose	Exposure, Potential confounder, subgroup identifier	Case records/eCRF	Details will be provided in Statistical Analysis Plan
RA treatment with Tofacitinib and/or other DMARDs - tolerability	Potential confounder, subgroup identifier	Case record/eCRF	Details will be provided in Statistical Analysis Plan
RA treatment with Tofacitinib and/or other DMARDs – route of administration	Potential confounder, subgroup identifier	Case record/eCRF	Details will be provided in Statistical Analysis Plan
Age	Baseline characteristic, potential confounder, sub-group identifier	Case records/eCRF	Details will be provided in Statistical Analysis Plan
Gender	Baseline characteristic, potential confounder, sub-group identifier	Case records/eCRF	Details will be provided in Statistical Analysis Plan
Height	Baseline characteristic, potential confounder, sub-group identifier	Case records/eCRF	Details will be provided in Statistical Analysis Plan
Weight	Baseline characteristic, potential confounder, sub-group identifier	Case records/eCRF	Details will be provided in Statistical Analysis Plan
Insurance Type	Baseline characteristic, Potential confounder, subgroup identifier	Case records/eCRF	Details will be provided in Statistical Analysis Plan
Date of first Diagnosis of RA	Baseline characteristic, potential confounder, sub-group identifier	Case records/eCRF	Details will be provided in Statistical Analysis Plan

Tofacitinib citrate

A3921302 OBSERVATIONAL PLAN NON-INTERVENTIONAL STUDY

Final, 23 August 2017

Smoking history and current smoking status	Baseline characteristic, potential confounder, sub-group identifier	Case records/eCRF	Details will be provided in Statistical Analysis Plan
Comorbidities	Baseline characteristic, potential confounder, sub-group identifier	Case records/eCRF	Details will be provided in Statistical Analysis Plan
Erythrocyte Sedimentation Rate (ESR) and C-Reactive Protein (CRP)	Baseline characteristics and outcome variable	Case records/eCRF	Details will be provided in Statistical Analysis Plan

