Rheumatoid Factor (RF), Anti-citrullinated protein antibodies (ACPA)	Baseline characteristic, potential confounder, sub-group identifier	Case records/eCRF	Details will be provided in Statistical Analysis Plan
Prognosis factors	Baseline characteristic, potential confounder, sub-group identifier	Case records/eCRF	Details will be provided in Statistical Analysis Plan
Prior drug treatment for RA	Potential confounder, sub-group identifier	Case records/eCRF	Details will be provided in Statistical Analysis Plan
Concomitant treatment of RA with Glucocorticoids	Potential confounder, sub-group identifier	Case records/eCRF	Details will be provided in Statistical Analysis Plan
Patient's Global Assessment of Arthritis	Baseline and outcome variable	Case records/eCRF	Details will be provided in Statistical Analysis Plan
Physician's Global Assessment of Arthritis	Baseline and outcome variable	Case records/eCRF	Details will be provided in Statistical Analysis Plan
Patient's Assessment of Arthritis Pain	Baseline and Outcome	Case records/eCRF	Details will be provided in Statistical Analysis Plan
Tender and swollen (28) joint count	Baseline and Outcome	Case records/eCRF	Details will be provided in Statistical Analysis Plan
Duration of Morning Stiffness	Baseline and Outcome	Case records/eCRF	Details will be provided in Statistical Analysis Plan
Functional Ability Questionnaire Hannover (FFbH)	Baseline and Outcome	Case records/eCRF	Details will be provided in Statistical Analysis Plan
EuroQoL EQ-5D-3L Health State Profile	Baseline and Outcome	Case records/eCRF	Details will be provided in Statistical Analysis Plan
Functional Assessment of Chronic Illness Therapy (FACIT) Fatigue Scale	Baseline and Outcome	Case records/eCRF	Details will be provided in Statistical Analysis Plan
Patient's satisfaction with drug treatment	Baseline and Outcome	Case records/eCRF	Details will be provided in Statistical Analysis Plan

Table 6 Variables

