7.5. Study procedure

Patients attending can be included by the HCP if they fulfil all selection criteria for the study and are started on treatment with Tofacitinib for moderate to severely active rheumatoid arthritis.

All visits shall be scheduled according to clinical practice. The treatment of a patient is independent from the patient enrolment into the study. Within this study 9 visits may be documented. At each visit patients will undergo procedures in compliance with the country label and as per standard of care. In order to collect comparable study data, visits 2 to 9 occurring +/- 14 days of the scheduled visit date will be used for data analysis.

After a training session the sites will get access to the eCRF, where the data and findings of the patient are documented. Additionally a folder with questionnaires will be provided. The collection of all data is prospective.

Dose and duration of treatment should be based on clinical and individual needs and are determined by the treating physician. To provide accurate information regarding the treatment, the initial Tofacitinib dose and all changes and the reasons for changes are documented during the course of the evaluation. The concomitant treatment of rheumatoid arthritis with Glucocorticoids is determined by the treating physician and is registered in the documentation sheet.

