7.6.2. Prognostic Factors

Prognostic factors will be determined at the Baseline Visit (Visit 1) based on prior medical history. The EULAR recommendation for the management of rheumatoid arthritis with synthetic and biological disease-modifying antirheumatic drugs [12] defines the following poor prognostic factors:

- Moderate (after conventional synthetic DMARD [csDMARD] therapy) to high disease activity according to composite measures
- High acute phase reactant levels
- High swollen joint counts
- Presence of RF especially at high levels
- Presence of ACPA, especially at high levels
- Combinations of the above
- Presence of early erosions
- Failure of two or more csDMARDs

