7.6.3. Insurance Type

Insurance type will be documented at the first visit (baseline visit). Patients can either have statutory health insurance or private insurance.

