7.3.3 POTENTIAL CONFOUNDERS TO BE INCLUDED IN THE PRIMARY ANALYSIS

A number of potential confounders will also be included in the primary analysis and all sensitivity analyses:

- Age at baseline
- Gender
- Duration of disease at baseline
- Indicator of tofacitinib dose
 - 1 if recommended dose of 5mg per day (i.e. TofInterval = BID),
 - 0 if reduced dose of 2.5mg per day (i.e. TofInterval = Daily).
- Poor prognostic factors (PF) indicator (1 if at least one Poor PF is present, 0 otherwise)
- Indicator of dose of MTX or combination partner (1 if increase in dose since last visit, 0 otherwise)
- Indicator of dose of Glucocorticoids (1 if increase in dose since last visit, 0 otherwise)
- Whether patient on 2nd or 3rd line treatment (see below)

A patient is defined as on 2nd line treatment if they were prescribed only csDMARDs prior to enrolling in the study.

A patient is defined as on 3rd line treatment if they were prescribed bDMARDs prior to enrolling in the study.

For a list of the medications considered to be csDMARDs and bDMARDs please see the eCRF.

- Indicator of tolerability issues (1 if treatment termination due to tolerability issues, 0 otherwise).
- Indicator of efficacy issues (1 if treatment termination due to efficacy issues, 0 otherwise).
- Incidence of the following comorbidities documented at the baseline visit (a term will be fitted for each comorbidity with the value 1 if the comorbidity is recorded for a patient or 0 otherwise):
 - Ischemic cardiovascular disease
 - Malignancies
 - Infections
 - Gastro disease
 - Osteoporosis
 - Depression

Any other variables observed to be potential confounders will also be investigated.

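### Insurance type, a protocol-named potential confounder, is in no SAP model, and prognosis enters only as an any-factor flag that is likely to be 1 for most patients

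*SAP*

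**What the plan says.** **Insurance type.** Protocol 7.3 (Table 6) gives it the roles of baseline characteristic, potential confounder and subgroup identifier, and leaves the operational definition to the SAP. The protocol's amendment table shows that it was added as a confounder by amendment 1. Protocol 7.6.3 records it at baseline with two levels: "Patients can either have statutory health insurance or private insurance". In the SAP it appears only in the schedule of activities.

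**Prognosis.** Table 6 has a row for prognosis factors and another for "Rheumatoid Factor (RF), Anti-citrullinated protein antibodies (ACPA", each with the role "Baseline characteristic, potential confounder, sub-group identifier". Protocol 7.6.2 lists eight poor prognostic items. The first is "Moderate (after conventional synthetic DMARD [csDMARD] therapy) to high disease activity according to composite measures" and the last is "Failure of two or more csDMARDs". SAP 7.3.3 turns the list into a single term: "Poor prognostic factors (PF) indicator (1 if at least one Poor PF is present, 0 otherwise". That confounder list applies to the primary analysis and to all sensitivity analyses.

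**Population.** Protocol 7.5 enrols patients who "are started on treatment with Tofacitinib for moderate to severely active rheumatoid arthritis". Inclusion criterion 3 requires eligibility under the product label. Protocol section 5 describes the indication as covering adults "who have responded inadequately to, or who are intolerant to one or more DMARD".

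**The concern.** The study's aim is to say which factors drive treatment decisions, and its evidence is a set of adjusted hazard ratios from observational data. A confounder therefore matters if it is related both to a factor (physician global, pain, satisfaction and so on) and to the decision to change treatment. The protocol treated insurance type as such a variable, yet no specified analysis adjusts for it or describes it. Serological and erosive prognosis could plausibly act in the same way. In the model they are represented only by a flag that many patients may satisfy through the disease activity that brought them into the study. A reader of the report would see prognosis named among the adjustment variables, and could take the adjustment to be fuller than it is.

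**Working it through.** **1. Where insurance type appears in the SAP.**

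| SAP section | Insurance type |
|---|---|
| 3.1 schedule of activities | listed |
| 7.3.1 factors, 7.3.2 sensitivity factors | absent |
| 7.3.3 confounders | absent |
| 6.6 subgroups | absent |
| 9.2.1 baseline summary list | absent |
| 9.2.6, all six recurrent-event model rows | absent |
| 2 amendments (departures from the protocol) | not mentioned |

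**2. Why the flag is likely to be 1 for most patients.** Protocol 7.6.2 counts moderate disease activity after a csDMARD, or high activity, as a poor factor. Protocol 5, 7.2.1 and 7.5 describe patients with moderate to severely active disease after at least one DMARD. A typical eligible patient meets the first item before RF, ACPA, erosions or csDMARD failures are considered, and each further item can only raise the share with flag = 1.

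**3. Size of the flag problem (prevalences assumed, since none is documented).** Let a be the share meeting the activity item and b the share with any other item, taken as independent. Flag prevalence is p = 1 − (1 − a)(1 − b). With b from 0 to 0.7:
- a = 0.80: p = 0.80 to 0.94
- a = 0.90: p = 0.90 to 0.97
- a = 0.95: p = 0.95 to 0.985
- a = 0.99: p = 0.99 to 0.997

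Information relative to a 50/50 covariate is p(1 − p)/0.25. The last column uses the planned 1500 patients.

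| p | p(1 − p) | relative information | flag = 0 of 1500 |
|---|---|---|---|
| 0.80 | 0.16 | 64% | 300 |
| 0.90 | 0.09 | 36% | 150 |
| 0.95 | 0.0475 | 19% | 75 |
| 0.98 | 0.0196 | 8% | 30 |
| 0.99 | 0.0099 | 4% | 15 |

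At p = 1 the coefficient cannot be estimated. At any p, the flag does not separate a patient with one poor factor from a patient with several.

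**4. What other model terms already cover.** Disease activity, acute-phase response and swollen joints are components or close relatives of the DAS28-4 (ESR) terms in SAP 7.3.1. Prior treatment is partly covered by the 2nd/3rd line indicator in 7.3.3. That indicator separates csDMARD-only patients from those with an earlier bDMARD, not one csDMARD failure from two or more. What remains is mainly RF/ACPA status, early erosions and number of csDMARD failures.

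**5. Rough size of the bias (inputs assumed).** To first order, the bias in a factor's log hazard ratio per SD is ln(HR of confounder) × p(1 − p) × d, where d is the difference in the factor's mean between confounder levels, in SD.
- Insurance, 10% private, HR 1.5 to 2.0, d = 0.3 to 0.5: 0.405 × 0.09 × 0.3 = 0.011, up to 0.693 × 0.09 × 0.5 = 0.031.
- Seropositivity, 60%, same HR and d: 0.405 × 0.24 × 0.3 = 0.029, up to 0.693 × 0.24 × 0.5 = 0.083.

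Benchmark from protocol 7.7: planned coefficient 0.01 per mm (absolute value) × SD 30.966 = 0.31 per SD for the physician global. Insurance is then 0.011/0.31 to 0.031/0.31, about 4% to 10%. Seropositivity is 0.029/0.31 to 0.083/0.31, about 9% to 27%, with the top figure needing both inputs at their extremes. The SD is that of change in the physician global, whereas the model uses its absolute value, so the benchmark is only a scale.

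**The case against.** - **The SAP need not fit everything in Table 6.** This stands. The table labels many variables as potential confounders (height, weight, smoking and route of administration are also not in SAP 7.3.3). The primary analysis in protocol 7.9.2.1 names no confounders, and protocol 7.9 allows the SAP to modify the plan. A reader might infer a breach of the protocol, and the documents do not support that. Insurance type has a stronger claim than the others because an amendment added it expressly as a confounder, so silence about it needs a reason.
- **SAP 7.3.3 ends with a promise to look into other variables that turn out to be confounders, and protocol 7.12 allows further sensitivity analyses.** These clauses name no variable and depend on the data. They promise investigation, not adjustment, so they do not pre-specify insurance type.
- **The baseline list in 9.2.1 may not be exhaustive.** True, but it does not put insurance type in any model. The list does include the presence of poor prognostic factors and ACPA/RF, so a near-constant flag would show up in the report, though only after the model is fixed.
- **The flag's prevalence is unknown.** This stands. Inclusion sets no DAS28 threshold, the factors are taken from prior history, and the eCRF recording rule is not shown. Under-recording could lower the share.
- **The bias figures may be too large.** This also stands. They use marginal differences, while the model already adjusts each factor for the others and for the listed confounders.

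**Conclusion.** The point holds in a limited form. It is a document fact that insurance type is missing from every specified model and from the baseline list without explanation. It is also a fact that prognosis is coded as any versus none. That the flag will be 1 for most patients is a deduction from the protocol's own definitions, not a documented figure. At an assumed prevalence of 90% to 99% it keeps 36% to 4% of the information of a balanced covariate.

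A reader might go further and infer that the flag is 1 for practically everyone, that it adjusts for nothing, or that the hazard ratios are not adjusted for prognosis at all. The documents do not support this: no prevalence is given, and the DAS28 terms and the treatment-line indicator carry part of prognosis. The residual gap is mainly RF/ACPA status, early erosions and number of csDMARD failures.

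The expected bias is modest. For insurance it is about 4% to 10% of the planned physician global effect, on assumed prevalence, hazard ratio and imbalance. The change is worth making because it is cheap, not because the primary result is shown to be unsafe.

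**What to change.** 1. In SAP 7.3.3 and in the confounder lists of 9.2.6, add insurance type (statutory or private) as an adjustment term. Add it to the baseline summary list in 9.2.1.
2. Replace the any-factor flag with separate terms for RF/ACPA positivity and failure of two or more csDMARDs, plus early erosions if the eCRF stores them as a separate item. Erosions appear only inside the prognostic-factor list in protocol 7.6.2, so item-level capture has to be checked first.
3. If a single term is preferred, use a count of poor factors that leaves out the disease-activity item and the item for combinations of the others. A raw count would keep the overlap with eligibility and count some factors twice.
4. Tabulate the prevalence of the any-factor flag, so that readers can see how much it could have adjusted for.

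Cost: SAP wording and three or four degrees of freedom in about 1500 patients. Insurance, RF/ACPA combined, csDMARD failures and erosions add four terms and the flag drops out, a net three; with RF and ACPA entered separately it is four. Insurance type, RF/ACPA and prior RA treatment are already separate protocol variables, so no new data collection is needed for those.

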6. RESEARCH QUESTION AND OBJECTIVES

The objective of this non-interventional study is to identify key factors that are driving treatment decisions by rheumatologists in the treatment of RA patients starting treatment with Tofacitinib in a real world setting. In addition to DAS28 score, the following factors may play an important role: difference between DAS28 at start of therapy and after 3-6 months, physician’s global assessment of disease activity, patient’s global assessment of disease activity, arthritis pain and patient’s satisfaction with drug treatment.

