7 ENDPOINTS AND COVARIATES

7.1 EFFICACY/ EFFECTIVENESS ENDPOINT(S)

7.1.1 PRIMARY ENDPOINTS

Number and timing of treatment escalations of tofacitinib patients in 24 months, where Treatment Escalation in this study is defined as a switch to another DMARD or combination of DMARDs when compared to the last visit.

The following types of escalations will be distinguished:

1. Treatment **Termination**, which is the termination of a DMARD (or multiple when on combination therapy) without starting a new DMARD therapy. Premature study terminations (without documented treatment termination) will not be considered treatment terminations.
2. Treatment **Step-up** which is an increase from the current treatment regime towards e.g. a combination of DMARDs
3. Treatment **Step-down**, which is a de-escalation from the current treatment regime, e.g. from combination therapy to monotherapy

Patients start their therapy at baseline with tofacitinib either in Monotherapy or in Combination therapy with MTX. Subsequent therapy changes are documented on eCRF instrument “Rheumatologische Medikation“ by:

- adding additional DMARDs on top of the current therapy
- stopping the current DMARD in monotherapy and adding a new DMARD
- stopping one of multiple DMARDs when on combination therapy
- stopping one of multiple DMARDs when on combination therapy and adding a new DMARD
- stopping all DMARDs and not starting a new therapy. The escalation types depend on the combination of DMARD classes (tsDMARD vs bDMARD vs TNFi vs csDMARD). The eCRF does not explicitly distinguish between tsDMARD vs bDMARD vs TNFi, but combines all rheumatic medications belonging to the above classes under

tsDMARD/bDMARD. For the definition of treatment escalations, the following assignment of rheumatic medication to DMARD classes will be done:

tsDMARDs:

- baricitinib
- upadacitinib
- filgotinib

TNFi:

- etanercept
- adalimumab
- certolizumab
- golimumab
- infliximab

bDMARDs (excluding TNFi):

- abatacept
- rituximab
- anakinra
- tocilizumab
- sarilumab

For details of treatment escalations, e.g., which DMARD class addition or reduction leads to a particular escalation type, see table 12.2 in section 12.1.2.

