12.1.2 DEFINITION OF TREATMENT ESCALATIONS

Table 11.2 provides an overview of all possible treatment switch combinations relevant for the analysis of the primary endpoint and defines the type of escalations, e.g., whether the treatment switch relates to a step-up, step-down or termination.

Table 12.2: Definition of treatment escalations

Therapy*	Mono Tofa	Mono tsDMARD	Mono csDMARD	MonoTNFi	Mono bDMARD	Combo+ csDMARD	Combo tsDMARD +csDMARD	ComboTNFi +csDMARD	Combo bDMARD+ csDMARD	Therapy Stop
MonoTofa	-	Step-up		Step-down	Step-up	Step-up	Step-up	Step-up	Step-up	Treatment termination
Mono tsDMARD	Step-up	Step-up if different tsDMARD		Step-down	Step-up	Step-up	Step-up	Step-up	Step-up	Treatment termination
Mono csDMARD	Step-up	Step-up	Step-up if different csDMARD		Step-up	Step-up	Step-up	Step-up	Step-up	Treatment termination
MonoTNFi	Step-up	Step-up		Step-down	Step-up if different TNFi	Step-up	Step-up	Step-up	Step-up	Treatment termination
Mono bDMARD	Step-up	Step-up		Step-down	Step-up	Step-up if different bDMARD	Step-up	Step-up	Step-up	Treatment termination
Combo+ csDMARD	Step- down	Step-up		Step-down	Step-up	Step-up	Step-up if different csDMARD	Step-up	Step-up	Treatment termination
Combo tsDMARD +csDMARD	Step-up	Step-up if different tsDMARD; Step-down otherwise		Step-down	Step-up	Step-up	Step-up if different tsDMARD or csDMARD	Step-up	Step-up	Treatment termination
Combo TNFi + csDMARD	Step-up	Step-up		Step-down	Step-down, if same TNFi, Step-up if different TNFi	Step-up	Step-up	Step-up if different csDMARD/TN Fi	Step-up if different bDMARD or csDMARD	Treatment termination
Combo bDMARD+ csDMARD	Step up	Step up		Step down	Step up	Step down if same bDMARD; Step-up otherwise	Step up	Step up	Step up	Step up if different bDMARD or csDMARD
*) Definitions:			Mono tsDMARD= Monotherapy any tsDMARD other than Tofa Mono csDMARD= Monotherapy any csDMARD Mono TNFi= Monotherapy any TNFi Mono bDMARD= Monotherapy any bDMARD other than TNFi Combo Tofa= Combination therapy tofacitinib with any csDMARD Combo csDMARD= Combination therapy tofacitinib + any csDMARD				Combo tsDMARD + csDMARD= Combination therapy tsDMARD other than tofacitinib + any csDMARD Combo TNFi + csDMARD= Combination therapy any TNFi+ any csDMARD Combo bDMARD + csDMARD= Combination therapy bDMARD other than TNFi+ anycsDMARD			

PPD

PPD

PPD

LEGAL DISCLOSURE

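### Both dose-increase indicators in SAP 7.3.3 look back over the same interval as the escalation, so adjusting for an increase decided together with a switch can attenuate the factor hazard ratios

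*SAP*

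**What the plan says.** **Event.** SAP 7.1.1 has an escalation "defined as a switch to another DMARD or combination of DMARDs when compared to the last visit". The qualifying changes it lists add or stop DMARDs, for example "adding additional DMARDs on top of the current therapy". Table 12.2 in SAP 12.1.2 classifies moves between drugs and classes; a move within a class counts only if the drug differs, as in "Step-up if different csDMARD". A higher dose of the same partner drug, or of a glucocorticoid, is therefore not an event, although no sentence says so outright.

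**Covariates.** SAP 7.3.3 lists "Indicator of dose of MTX or combination partner (1 if increase in dose since last visit, 0 otherwise" and "Indicator of dose of Glucocorticoids (1 if increase in dose since last visit, 0 otherwise". It introduces the list with "A number of potential confounders will also be included in the primary analysis and all sensitivity analyses". The summary table in SAP 9.2.6 repeats both terms in every primary and sensitivity row.

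**Objective.** Protocol 6 sets out "to identify key factors that are driving treatment decisions by rheumatologists". The factors are two DAS28 terms, physician and patient global assessment, pain and satisfaction (SAP 7.3.1).

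**The concern.** The event and the two indicators share one look-back, the period since the last visit. SAP 9.1.1 puts status and covariates on one row per period. Nothing says whether the dose change came before the factors were measured, between measurement and switch, or with the switch.

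The order decides what the indicator is. Before the current factor values, an increase is a prior cause and belongs in the model. Decided with the switch, it is a response to the same DAS28, pain and global scores, and conditioning on it removes part of the association that the study wants to estimate. Two situations make this plausible:

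- a glucocorticoid increase that bridges a switch;
- MTX added to tofacitinib monotherapy. This is a step-up under Table 12.2, and the SAP does not say whether going from no dose to a dose is an increase. If it is, the covariate is part of the event.

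The factor hazard ratios are the study's answer. No planned model omits the indicators, and SAP 9.1.1 does not present estimates for confounders, so a reader could not see what the two terms do.

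**Working it through.** **1. Timing rules in the plan**

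| Item | Rule | Place |
|---|---|---|
| Escalation | compared with the last visit; between-visit events assigned by window | SAP 7.1.1, 9.2.2, 12.1.1 |
| Dose indicators | increase since the last visit | SAP 7.3.3 |
| Missing covariates | value nearest the event, the later one on ties | SAP 8.1 |
| Timing sensitivity analysis | the switch moves to the prior visit; nothing is said about the indicators | SAP 9.2.2 |
| Dose data | documented at each visit; start and stop dates required for DMARD switches; no date for a glucocorticoid dose change | Protocol 7.6.5, 7.6.6 |

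No row orders dose change, factor measurement and switch.

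**2. The plan's own figures.** None bears on this point. The study-size simulation (Protocol 7.7) has five factors and no dose covariate. All rates below are assumptions.

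**3. Increase accompanies switch.** Inputs, one row per visit:

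- DAS28 x ~ N(3.5, 1.2²).
- P(switch) = expit(a + 0.6(x − 3.5)), with a set to give 10% per visit.
- Rows without a switch: P(increase) = expit(b + 0.6(x − 3.5)), with b set to give 5%.
- Rows with a switch: P(increase) = c.
- Fit log(−log(1 − p)) = β0 + β1·x + β2·(increase); HR per DAS28 point = exp(β1).

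| | Headline run | Repeat with the inputs above (400,000 rows) |
|---|---|---|
| Without the indicator | 1.75 | 1.73 |
| With it, c = 10% | 1.73 | 1.71 |
| With it, c = 30% | 1.56 | 1.54 |
| With it, c = 50% | 1.40 | 1.39 |

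On the log scale, ln 1.75 = 0.560, ln 1.56 = 0.445 and ln 1.40 = 0.336. The coefficient shrinks by 1 − 0.445/0.560 = 21% and by 1 − 0.336/0.560 = 40%.

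The size also depends on increases outside switches following DAS28. With that slope at 0 instead of 0.6, the repeat run falls only from 1.73 to 1.69 (c = 30%) and 1.63 (c = 50%).

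**4. Wider range of rates.** The planning rate of 3.16 baseline events per patient is 3.16/8 = 0.395 per interval over eight intervals, so 10% may be low. A second simulation (60,000 patients, 8 visits) assumed HR 1.5 per SD of a factor for any intensification, 10–40% intensification per visit, and switches as 30–70% of these.

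| Model for switch | HR per SD |
|---|---|
| Without the indicator | 1.39–1.50 |
| With it, 20% co-occurrence | 1.40–1.47 |
| With it, 50% | 1.23–1.27 |
| With it, 80% | 1.08–1.11 |
| Event is switch or dose increase | 1.49–1.51 |

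The pattern is the same: little effect at low co-occurrence, clear attenuation at high.

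**5. Increase precedes the factor values.** With a true HR of 1.5, the adjusted HR is 1.49–1.51 and the unadjusted one 1.39–1.55. Here adjustment is right and omission biases.

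**6. Increase replaces switch.** Three-way choice per visit, 10% switch and 10% increase, log-odds 0.6 for both: HR 1.61 unadjusted and 1.74 adjusted. With no dose-increase option, the same coefficient gives 1.74. The adjusted value recovers the coded effect and the unadjusted one is diluted.

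**The case against.** The strongest reply is that the indicators may be doing their proper job. The look-back also covers an increase made at or just after the previous visit, before the current scores. Such an increase can change both the scores and the chance of a switch, and step 5 of the working shows that leaving it out would bias the result. Protocol 7.3 already named DMARD dose and glucocorticoids as potential confounders. This stands: the defect is the missing order, not the wish to adjust for dose.

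It can also be said that SAP 9.2.2 plans an analysis with switches assigned to the prior visit, and a collinearity check. These help only in part. The first moves the switch but gives no timing for the indicators; the second does not tell a confounder from a consequence.

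The simulations use a continuous DAS28 term alone, whereas the primary model has two binary DAS28 terms, four other factors and further confounders. That is fair, and the figures are illustrations only.

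A reader might infer four stronger points that the documents do not support:

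- *Increases are made at the same visit as the switch.* No passage says so.
- *The hazard ratios are distorted.* They can be; this depends on unknown co-occurrence and timing.
- *They are biased upward when increases replace switches.* Step 6 does not show this.
- *Dose increases should have been primary events.* The objective speaks broadly of treatment decisions, but protocol and SAP both define the event as a DMARD switch, and the overall event includes step-downs and terminations. It was not designed to measure intensification alone.

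**Conclusion.** The concern holds as a gap in timing. SAP 7.3.3 adjusts every planned model for dose increases over the interval in which the escalation is counted, without ordering them against the factor assessment and the switch. Where increases are decided together with switches, the factor hazard ratios can be attenuated: under the assumptions of step 3, from about 1.75 per DAS28 point to about 1.56–1.40 at 30–50% co-occurrence, with little change at about 10%. The loss is smaller if increases outside switches do not follow disease activity. Co-occurrence and timing are not given in the documents, so the actual size is unknown.

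The clearest single item is the undefined coding when a partner drug is started or changed, because there the covariate may be part of the event. The point is worth correcting because it touches the study's main estimates and the repair is cheap. It does not show that the planned result will be wrong.

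**What to change.** In SAP 7.3.3, and in the matching rows of 9.2.6:

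1. Lag both indicators so that they reflect only changes in force by the previous visit, or, where a date is recorded, changes dated before the factor assessment. State the value for the first interval, which has no earlier visit pair. In the prior-visit analysis of SAP 9.2.2, count the lag from the visit to which the switch is assigned.
2. State that starting or changing a partner drug that is itself the escalation does not set the indicator to 1.
3. Add one sensitivity model without the two indicators, so that their influence can be seen.

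Optionally, add a supportive model whose event is a step-up or a dose increase. The primary event definition is unchanged, and no dosing rule is implied.

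**Cost.** A few sentences in the SAP, two re-derived covariates and one extra model, using doses already documented at each visit. The drawback is that lagging may miss increases made between visits but before the factor assessment, which are genuine confounders. Comparing the lagged model with the one that omits the indicators helps to judge how much the handling of these terms matters.
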